8.2 Pre-Operative Evaluation

All subjects will complete the ODI, VAS, and SF-12v2 questionnaires within 90 days prior to the scheduled surgery. All patient questionnaires should be completed during the visit, preferably prior to the patient interacting with the Investigator or other clinical staff. A pertinent medical history will be documented and all subjects will undergo a standard neurological examination including assessments of sensation, motor function, and reflexes.

8.2.1 Pre-Operative Assessment

- Informed consent
- Inclusion/exclusion criteria
- Demographics
- Pertinent history and physical including current symptoms, height, weight, and tobacco use
- Functional, Economic and Work/school status
- Current medication for spine problem
- Neurological Examination
 - AP and Lateral x-rays, (must be completed within 180 days of planned date of surgery)
 - MRI (optional per standard of practice within 180 days of planned date of surgery)
- Oswestry Disability Index; Back, Hip/Buttock, and Leg VAS; and SF-12v2 (within 90 days of planned date of surgery)

8.3 Hospitalization/Surgical Technique/Discharge

Subjects will be admitted to the hospital according to the Investigator's standard for an instrumented posterolateral fusion in conjunction with a TLIF surgery. Prophylactic antibiotics, preoperative planning, patient positioning and anesthesia will be carried out in accordance with the institution's and Investigator's standard of care.

Surgical Approach. The surgeon performs a midline incision and standard posterior exposure to decorticate the transverse processes bilaterally to accommodate graft for the posterior fusion. The spinous processes and interspinous ligaments can usually be left intact, which minimizes epidural scarring and provides a larger surface area for the posterior fusion.

After exposure, the EVEREST Spinal System pedicle screws are placed bilaterally in accordance with K2M's Instructions for Use and Surgical Technique Manual. Fluoroscopy or other strategies may be used to aid in proper screw positioning. Distraction may then be performed using the surgeon's preferred method to open the posterior portion of the disc space, if needed.

Transforaminal Lumbar Interbody Fusion (TLIF). For the TLIF procedure, access to the disc space is gained via a triangular working window. The window is formed by the traversing nerve root and thecal sac on the medial side, the exiting nerve root from the proximal vertebral level on the lateral side, and the superior aspect of the pedicle of the distal vertebra forms the base of the triangle. The surgeon performs a laminotomy, laminectomy and/or facetectomy (partial or total) along with removal of the ligamentum flavum to provide access to the disc space. Care should be taken to preserve the facets as much as possible and remove only enough bone as needed to provide access for introduction of the interbody spacer and to decompress and mobilize the nerve root as necessary. If decompression of the contralateral side of the spinal canal is required, the TLIF procedure can be modified to include a central laminectomy.

After exposure of the posterior aspect of the disc, an incision is made in the annulus through which the discectomy and endplate preparation are performed. Endplate preparation consists of removal of the cartilaginous endplate down to bleeding bone. The interbody spacer (a biocompatible PEEK spacer of the surgeon's choice) is then introduced.

The TLIF approach with the EVEREST Spinal System also allows for auxiliary procedures for decompression of the spinal cord, correction of spondylolisthesis, correction of disc space collapse or mild kyphosis, as may be medically indicated.

Once the interbody implant is in place and bone graft added to the disc space, distraction is released and compression is applied to the pedicle screw to load the anterior implant and restore lordosis to the spine.

Posterolateral/Transverse Process Fusion and use of VESUVIUS Demineralized Fibers. For each level of the posterolateral fusion, local bone (amount used is to be estimated and recorded) is supplemented with VESUVIUS Demineralized Fibers and bone marrow aspirate (BMA)². The Fibers and BMA are to be combined in a 3:2 volumetric ratio (i.e., a minimum of 15cc Fibers and 10ml BMA are required for a one-level case). If BMA volumes are insufficient to achieve a 3:2 ratio, BMA may be supplemented with venous-line blood. The bone graft, extended with a minimum of 15cc VESUVIUS Fibers and 10ml BMA per level, is then evenly distributed to the right and left lateral gutters. Local bone may be obtained from the levels to be fused, as well as from no more than one additional level of decompression above the target level(s).

The interspinous ligament, if preserved, will serve to prevent graft migration into the exposed portion of the spinal canal and foramen. Care must be taken when placing graft on the ipsilateral intertransverse region to avoid allowing graft to enter the spinal canal or compress the exiting nerve root. Before closure, inspect the neurologic elements to ensure that no graft material has fallen into the spinal canal.

² Obtained from the anterior iliac crest and/or vertebral body (refer to detailed instructions provided in Appendix 1 of this protocol)

Surgical Close and Recovery. Standard procedures and precautions are to be followed for closure of the surgical incision and postoperative recovery. The patient is typically mobilized out of bed the day after surgery; bracing is not required but can be used according to surgeon preference. The subject may be instructed to return to normal activity at the discretion of the Investigator.

Additional post-operative restrictions may be imposed according to the standard of care normally utilized by the Investigator. In addition, subjects should be instructed to notify the Investigator if experiencing untoward events including but not limited to noticeable pain, numbness, tingling, or weakness that does not decrease with rest, swelling of the lower extremities that does not decrease, or increased pain, erythema, edema or drainage from the surgical incision. The Investigator should then determine if an evaluation is warranted.

A Subject may be withdrawn from the study intra-operatively at the discretion of the Investigator if unexpected findings/occurrences dictate deviation from the intended study procedure. Justification for an intra-operative withdrawal and alternative surgical procedure must be fully documented in the subject's medical record and on the Study Exit case report form.

8.3.1 Surgery/Hospital Discharge Evaluation

Surgery Data – Data points required on the Operative case report form must be documented at the time of surgery, including intra-operative adverse events.

- Date of Hospital Admission
- Date of Surgery
- Date of Hospital Discharge
- Implanting Surgeon
- Implanted System Details (screw and rod size, connector use, etc.)
- Surgery Detail/Concomitant Procedures
- Surgery Time (initial incision to closure)
- Anesthesia Time
- Perioperative Antibiotic Use
- Estimated Blood Loss
- Quantity of VESUVIUS Demineralized Fibers, Bone Marrow Aspirate and Local Bone Used
- Adverse Event Assessment

If the patient experienced an adverse event(s) during the hospitalization it should be documented and recorded on an Adverse Event case report form.

8.4 Post-Operative Follow-Up Visits

All subjects will be required to return for follow-up visits at initial post-op, 3 months, 6 months, and 12 months, and 24 months post-procedure. (A "wound check only" visit does not require data collection unless there is an adverse event. Then this would be captured as an Unscheduled Visit, and an Adverse Event CRF would be completed.)

Data collected at each follow-up visit must be confirmable by source documents and the appropriate case report forms must be completed. All patient questionnaires should be completed at the visit, preferably prior to the patient interacting with the Investigator or other clinical staff. Post-operative follow-up visit requirements are as follows:

8.4.1 Follow-Up Evaluation Data – Post-op through 24 Months

- Functional, Economic and Work/school Status (including release for return to work/school) (initial post-op, 3 month, 6 month, 12 month, and 24 month)
- Current Symptoms (all visits)
- Medication (taken for spine problem since last contact) (initial post-op, 3 month, 6 month, 12 month, and 24 month)
- Neurological Examination (initial post-op, 3 month, 6 month, 12 month, and 24 month)
- AP, Lateral, Oblique and Flex/Ext x-rays (6 month, 12 month, and 24 month)
- Oswestry Disability Index (initial post-op, 3 month, 6 month, 12 month, and 24 month)
- Back, Hip/Buttock, and Leg VAS (initial post-op, 3 month, 6 month, 12 month, and 24 month)
- SF-12v2 (initial post-op, 3 month, 6 month, 12 month, and 24 month)
- Adverse Event Assessment (all visits)
- CT Scan (12 month)
- Patient Satisfaction (12 month, 24 month)
- Study Exit

8.5 Unscheduled Follow-up Evaluation

Subjects may return to the clinic at a time point that is not a scheduled follow-up visit. If the Investigator determines that the return visit is related to the study device, procedure or surgery, the Unscheduled Visit portion of the Post-Operative Follow-Up case report form should be completed. If a subject requires a device or procedure related re-operation including supplemental fixation, revision and/or device removal as a result of an unscheduled visit the Sponsor should be notified immediately and an Adverse Event case report form should also be completed.

8.6 Schedule of Subject Evaluations

Interval → Assessment ↓	Pre-op	Operative/ Discharge	Initial F/U (discharge-8 weeks post-op)	3 Month F/U (± 2 weeks)	6 Month F/U (± 1 month)	12 Month F/U (± 2 months)	24 Month F/U (±2 months)	Unscheduled Visit
Informed Consent	X							
Inclusion/Exclusion	X							
Demographics	X							
Pertinent History	X							
Current Symptoms / Complaints & Findings	X		X	X	X	X	X	
Functional, Econ., Work/school Status	X		X	X	X	X	X	
Medications for Spine Problems	X		X	X	X	X	X	
Neurological Examination	X		X	X	X	X	X	
ODI	X		X	X	X	X	X	
Back, Hip/Buttock, and Leg VAS	X		X	X	X	X	X	
SF-12v2	X		X	X	X	X	X	
Patient Satisfaction						X	X	
Hospitalization and Surgery Data		X						
Adverse Event Assessment		X	X	X	X	X	X	X
AP & Lateral x-rays	X				X	X	X	If needed
Flex/Ext x-rays					X	X	X	
Oblique (right, left) x-rays					X	X	X	
CT Scan						X		
Study Exit							X	

8.7 Pregnancy During Study Participation (as appropriate)

If a subject becomes pregnant during the study, the sponsor should be notified as soon as possible. The subject will remain in the study, but during the pregnancy the study follow-up visit(s) will be modified to exclude the X-ray imaging requirements. At follow-up visits after the pregnancy, the required X-rays should again be performed. Information related to the pregnancy and outcome should be maintained by the site and documented by the Sponsor in monitoring reports during periodic visits.

8.8 Protocol Deviations

The Protocol must be followed closely, and the Investigators should not deviate from the protocol unless in the opinion of the Investigator a deviation from the protocol is in the best interest of safety for the subject. A deviation from the protocol should be reported to the sponsor as soon as possible after the deviation is noted. In addition, during routine monitoring visits the monitor may determine a protocol deviation and initiate the protocol deviation process. All protocol deviations must be documented on a Protocol Deviation case report form. For the scientific integrity of the study, protocol deviations must be kept at a minimum. If the site has an unacceptable number of protocol deviations that cannot be explained due to patient safety, the issue will be discussed with the site and corrective action will be considered.

In the event a patient questionnaire is not completed during a visit, permission may be obtained from the Sponsor to have the questionnaire mailed into the site within a reasonable amount of time.

8.9 Subject Lost to Follow-Up

Every attempt will be made to have all subjects complete the follow-up visit schedule as specified in the protocol. A subject will not be considered lost to follow-up unless efforts to obtain compliance are unsuccessful. If a subject misses a follow-up visit, the site must document attempts to contact the subject by phone twice. If both contact attempts are unsuccessful, a certified letter from the Investigator must be sent to the subject's last known address indicating the subject's commitment to the study and site contact information to arrange a visit. If the subject does not respond, only then will the subject be considered lost to follow-up. If a subject is lost to follow-up, a Study Exit case report form, including a full description of the attempts to locate the subject, must be completed.

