6 STUDY ENDPOINT

6.1 Primary Study Endpoint

The endpoint of this study is the fusion status at 24 months.

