7.3 Study Duration

Study subjects will be expected to participate in this study for 24 months following surgery, with follow-up evaluations at initial post-op, 3 months, 6 months, 12 months, and 24 months.

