12.2 Study Hypotheses

The primary study endpoint is the rate of fusion at 24 months. The primary hypothesis of this trial is that the fusion rate with the VESUVIUS Demineralized Fibers and the EVEREST Spinal System combination is non-inferior to the fusion rate achieved and reported with the traditional fusion utilizing autograft and posterior stabilization.

A PubMed literature review was conducted to assemble relevant publications utilizing results from posterior fusion surgeries incorporating osteobiologics. Searches included all peer-reviewed journals published between January 2000 and April 2013. Sample sizes, patient populations, evaluated variables, results, and recorded complications were assessed for each selected article. Only articles describing the use of autograft in comparable patient populations were incorporated into the results. The following table gives the fusion rates found during the literature review:

Papers*	Number of Cases	Number of Fusions	Fusion Rate
Paper 1 ¹	81	44	54.3%
Paper 2A ²	39	34	87.2%
Paper 2B	35	29	82.9%
Paper 3 ³	36	15	41.7%
Paper 4 ⁴	45	33	73.3%
Paper 5A ⁵	21	19	90.5%
Paper 5B	22	20	90.9%
Paper 6A ⁶	10	10	100.0%
Paper 6B	10	10	100.0%
Paper 7A ⁷	47	44	93.6%
Paper 7B	48	42	87.5%
Paper 8A ⁸	42	31	73.8%
Paper 8B	42	24	57.1%
Pooled	478	355	74.3%

* Refer to Appendix 2 for references

A total of 355 successes in 478 subjects gives an overall fusion rate of 74.3%. The hypotheses to be tested for this primary endpoint are as follows:

$$H_0: P_{K2M} \leq P_0 - \delta$$

$$H_A: P_{K2M} > P_0 - \delta$$

where P_{K2M} is the success rate of the VESUVIUS Demineralized Fibers and the EVEREST Spinal System combination, P_0 is the literature success rate of 74.3% and δ is the non-inferiority margin of 10% against the historical success rate.

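### Section 8.9 lets a subject be exited as lost after one missed early visit and does not require a further attempt at 24 months, when the primary endpoint is read

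*Combined protocol and SAP*

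**What the plan says.** Section 8.9 opens with an intention: "Every attempt will be made to have all subjects complete the follow-up visit schedule as specified in the protocol". The steps that follow are these:

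- **Trigger:** "If a subject misses a follow-up visit, the site must document attempts to contact the subject by phone twice". The section does not limit this to particular visits or ask for consecutive misses.
- **Second step:** "If both contact attempts are unsuccessful, a certified letter from the Investigator must be sent to the subject's last known address". The letter must tell the subject how to reach the site to arrange a visit.
- **Declaration:** "If the subject does not respond, only then will the subject be considered lost to follow-up".
- **Consequence:** the exit form becomes mandatory, in a sentence that begins "If a subject is lost to follow-up, a Study Exit case report form, including a full description of the attempts to locate the subject, must".

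Section 7.3 sets the visits: "follow-up evaluations at initial post-op, 3 months, 6 months, 12 months, and 24 months". Section 6.1 states: "The endpoint of this study is the fusion status at 24 months". Section 12.2 agrees: "The primary study endpoint is the rate of fusion at 24 months". The schedule in section 8.6 places Study Exit in the 24-month column only.

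Section 8.9 gives no waiting period before loss is declared, no renewed contact at later windows and no route back after exit. It also contains no bar on a subject who returns.

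**The concern.** A site that follows section 8.9 to the letter can exit a subject who misses the 3-month visit and answers neither the calls nor the letter. That is about 21 months before the only reading that decides the trial. A subject who is unreachable for a few weeks may be reachable again later, but the protocol requires nobody to try.

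Two things are at stake. The first is the number of 24-month fusion readings, and so power. The second is bias. If subjects lost this way fuse at a different rate from those who stay, the observed rate shifts, and section 12.5 tests that rate against a fixed 64.3%. In a randomised trial a similar loss pattern in both arms could partly cancel. Here there is no second arm.

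**Working it through.** **1. Reading the rule against the endpoint.** There are five post-operative visits, and four of them (initial, 3, 6 and 12 months) precede month 24. Section 8.9 applies alike to all five. For a miss at any of the first four, the procedure can end in exit with the primary reading still ahead. For a miss at the 24-month visit, exit costs no later reading. Section 8.6 expects exit at month 24, so an exit under 8.9 can come earlier than the schedule otherwise has it.

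**2. The plan's own power figure.** Inputs from sections 12.2, 12.3 and 12.5: historical rate 74.3%, margin 10%, hence a bar of 0.743 − 0.10 = 0.643; one-sided exact binomial test at 0.05; assumed true rate 0.743; 173 subjects stated to give more than 80% power.

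The critical count r is the smallest value with P(X ≥ r | n, 0.643) ≤ 0.05. Power is P(X ≥ r | n, 0.743). For n = 173, r = 123, the exact level is 0.0354 and power is 85.3%. The stated figure is reproduced.

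**3. Illustration of recovered readings.** *Assumptions:* 204 treated; 204 − 173 = 31 lost (15.2%, close to the 15% dropout in section 12.3); analysis of evaluable subjects only; fusion unrelated to loss; true rate 74.3%. The documents do not say how many losses are recoverable, so a range is shown.

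| Recovered of 31 | Evaluable n | Critical count | Power |
|---|---|---|---|
| 0 | 173 | 123 | 85.3% |
| 5 | 178 | 126 | 87.6% |
| 10 | 183 | 129 | 89.5% |
| 21 | 194 | 137 | 89.4% |
| 31 | 204 | 143 | 92.5% |

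Power does not rise smoothly because the exact test moves in whole counts.

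**4. Illustration of bias.** *Assumptions:* the true rate in all subjects is exactly 64.3%, so that success would be a false positive; 15% are lost; 173 are evaluable; lost subjects fuse at rate q. The rate among those observed is (0.643 − 0.15q) / 0.85, and false success is P(X ≥ 123 | 173, that rate).

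| q among the lost | Observed rate | Chance of false success |
|---|---|---|
| 64.3% (no bias) | 64.3% | 3.5% |
| 54.3% | (0.643 − 0.08145) / 0.85 = 66.1% | 9.3% |
| 44.3% | (0.643 − 0.06645) / 0.85 = 67.8% | 20.2% |
| 74.3% | (0.643 − 0.11145) / 0.85 = 62.5% | 1.1% |

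The bias can run either way, and the documents do not indicate which. The table shows what 15% total loss could do. It does not show the part that section 8.9 causes.

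**The case against.** The strongest defence is that section 8.9 sets minimum steps before loss may be declared. It commits to every attempt at completion, requires two calls and a certified letter, and sets no deadline. A site could wait through later windows and still comply, and a subject who answers any contact is not lost. All of that is correct. It does not close the gap, because the stated intention leads to steps that end in exit. A site that stops after the letter is equally compliant, and nothing requires an attempt at month 24.

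A reader might infer that the protocol discards later data, or that one missed visit by itself means exit. The documents support neither. No text refuses a returning subject or excludes a later image, and exit needs three unanswered contacts as well as the missed visit.

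A reader might also attribute a collapse in power to this rule. If all 204 stay in the denominator and missing counts as not fused, 143 fusions are needed, and power with 31 lost is 0.6%. That figure comes from a different gap: sections 12.4 and 12.5 state no missing-data rule for the fusion analysis. It would arise under any retention wording. Even with 10 of the 31 recovered, power on that convention would be only 13.4%.

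Finally, 15% dropout is already planned for, and 173 evaluable subjects exceed the 80% target. This stands as far as power goes, provided evaluable subjects are analysed. Planning for loss gives no protection against bias and is no reason to keep avoidable loss.

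The 15% is also not broken down. It may include withdrawal of consent (section 8.10) or intra-operative withdrawal (section 8.3), which 8.9 does not govern.

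**Conclusion.** The point holds as a risk of avoidable missing primary outcomes. Section 8.9 permits lost status, and then requires exit, after any one missed visit with two calls and a certified letter unanswered. It does not require renewed contact through the 24-month window.

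The number of readings at risk cannot be derived from the documents. On the assumption that 10 of 31 losses are recovered, evaluable-only power rises from 85.3% to 89.5%, a gain of about 4 percentage points. The benefit for bias may matter more in a single-arm design, but its size and direction are unknown. This is a cheap improvement worth making. It does not show that the trial is underpowered or that collected data are thrown away.

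**What to change.** Amend section 8.9 as follows:

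- Record a missed visit with unanswered contacts as a missed visit.
- Repeat the contact attempts at each later scheduled window, up to and including 24 months.
- Assign lost-to-follow-up status and complete the Study Exit form only after the 24-month window closes without contact, unless the subject has withdrawn consent under section 8.10 or has died.
- State that subjects who reappear stay in the study and that their 24-month images are used.

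This brings 8.9 into line with its own opening sentence and with the timing of Study Exit in section 8.6. The cost is protocol wording, a few extra calls by existing site staff for the subjects who miss a visit, and later completion of some exit forms. The missing-data rule for the fusion analysis needs its own correction, which this change does not replace.

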8.10 Subject Withdrawal

Subjects have the right to withdraw their consent at any time during the study. If a subject requests to withdraw from the study, all information regarding the subject's withdrawal and disposition must be recorded in the subject's medical record. A Study Exit case report form, including a full description of the circumstances related to the withdrawal, must be completed.

8.11 Study Case Report Forms

The Sponsor will provide Case Report Forms (CRFs) to the sites for the study. Visit or evaluation specific as well as additional CRFs to complete as needed are included. Data should be entered with a black pen on the specified locations of the CRFs. If an error is made on a CRF, the incorrect entry should be crossed out with a single horizontal line, the correct entry written next to it, and the correction initialed and dated by the person making the correction. Copies of the CRFs for the study are included as an appendix to the protocol.

List of Case Report Forms

- Inclusion/Exclusion
- Pre-operative
- Operative/Discharge
- Follow-up form covering:
 - Initial Post-Op Follow-up Visit (discharge to 8 weeks post-op)
 - 3 Month Follow-up Visit ± 2 weeks

- 6 Month Follow-up Visit \pm 1 month
- 12 Month Follow-up Visit \pm 2 months
- 24 Month Follow-up Visit \pm 2 months
- Unscheduled Visit
- Subject Questionnaires including Oswestry Disability Index; Back, Hip/Buttock, and Leg Visual Analog Scale (VAS); SF-12v2; and Patient Satisfaction
- Adverse Event
- Protocol Deviation
- Study Exit

